## 9.7. Genetics

A blood sample will be collected for pharmacogenetic analysis as specified in the Schedule of Activities (Section 2), where local regulations allow.

Samples will not be used to conduct unspecified disease or population genetic research either now or in the future. Samples will be used to investigate variable exposure or response to LY3074828 and to investigate genetic variants thought to play a role in autoimmune and inflammatory diseases. Assessment of variable response may include evaluation of AEs or differences in efficacy.

All samples will be coded with the subject number. These samples and any data generated can be linked back to the subject only by the investigative site personnel.

Samples will be retained for a maximum of 15 years after the last subject visit, or for a shorter period if local regulations and/or IRB impose shorter time limits, for the study at a facility selected by Lilly or its designee. This retention period enables use of new technologies, response to regulatory questions, and investigation of variable response that may not be observed until later in the development of LY3074828 or after LY3074828 is commercially available.

Molecular technologies are expected to improve during the 15 year storage period and therefore cannot be specifically named. However, existing approaches include whole genome or exome sequencing, genome wide association studies, multiplex assays, and candidate gene studies. Regardless of technology utilized, data generated will be used only for the specific research scope described in this section.

## 9.8. Biomarkers

This section is not applicable for this study.

## 9.9. Health Economics

This section is not applicable for this study.

## 10. Statistical Considerations and Data Analysis

### 10.1. Sample Size Determination

Approximately 54 subjects (18 per treatment arm) may be enrolled to allow evaluable data from 16 subjects from each treatment arm to be obtained. The estimated total variability (coefficient of variation) in  $AUC(0-\infty)$ ,  $AUC(0-t_{last})$ , and maximum observed drug concentration ( $C_{max}$ ) was 49%, 49%, and 23%, respectively, in Study AMAA following a single SC dose of 120 mg LY3074828. The coefficient of variation of 49% was used for precision estimates and is assumed for all treatment arms. A sample size of 48 subjects will provide a precision, in log scale, of approximately 0.32 for the geometric means ratio in  $AUC(0-\infty)$ ,  $AUC(0-t_{last})$ , and  $C_{max}$  of lyophilized to solution formulation in log scale. That is, there is a 90% probability that the half-length of the 90% confidence interval (CI) of the geometric means ratio in log scale is not larger than 0.32. Subjects who are randomized but not administered treatment, or subjects (maximum of 6) that are administered treatment but do not have PK and ADA samples collected up to and including Day 57, may be replaced to ensure that approximately 16 subjects from each treatment arm may complete the study.

### 10.2. Populations for Analyses

#### 10.2.1. Study Participant Disposition

A detailed description of subject disposition will be provided at the end of the study.

#### 10.2.2. Study Participant Characteristics

The subject's age, sex, weight, BMI, height, race/subrace, and other demographic data will be summarized by treatment and overall.

### 10.3. Statistical Analyses

Statistical analysis of this study will be the responsibility of Eli Lilly and Company or its designee.

Pharmacokinetic analyses will be conducted on the full analysis set. This set includes all data from all randomized subjects receiving the dose of LY3074828 with evaluable PK data, according to the treatment the subjects actually received. Safety analyses will be conducted for all subjects receiving a dose of LY3074828, whether or not they completed all protocol requirements.

Additional exploratory analyses of the data will be conducted as deemed appropriate. Study results may be pooled with the results of other studies for population PK analysis purposes to avoid issues with post-hoc analyses and incomplete disclosures of analyses.

No adjustments for multiple comparisons will be made.

### 10.3.1. Safety Analyses

#### 10.3.1.1. Clinical Evaluation of Safety

All investigational product and protocol procedure AEs will be listed, and if the frequency of events allows, safety data will be summarized using descriptive methodology.

The incidence of symptoms for each treatment will be presented by severity and by association with investigational product as perceived by the investigator. Symptoms reported to occur prior to study entry will be distinguished from those reported as new or increased in severity during the study. Each symptom will be classified by the most suitable term from the medical regulatory dictionary.

The number of investigational product-related SAEs will be reported.

#### 10.3.1.2. Statistical Evaluation of Safety

Safety parameters that will be assessed include clinical laboratory parameters, vital signs, and ECG parameters. The parameters, and changes from baseline (predose) where appropriate, will be listed, and summarized using standard descriptive statistics. Additional analysis will be performed if warranted upon review of the data.

### 10.3.2. Pharmacokinetic Analyses

#### 10.3.2.1. Pharmacokinetic Parameter Estimation

Pharmacokinetic parameter estimates for LY3074828 will be calculated by standard noncompartmental methods of analysis.

The primary parameters for analysis will be  $AUC(0-\infty)$  and  $AUC(0-t_{last})$  for LY3074828. The secondary parameters for analysis will be  $C_{max}$  and time of  $C_{max}$  ( $t_{max}$ ) of LY3074828. Dose-normalized (DN)- $AUC(0-\infty)$ , DN- $AUC(0-t_{last})$ , and DN- $C_{max}$  will be calculated. Other noncompartmental parameters, such as  $t_{1/2}$ , apparent total body clearance of drug calculated after extra-vascular administration (CL/F), and apparent volume of distribution during the terminal phase after extra-vascular administration ( $V_z/F$ ) may be reported.

#### 10.3.2.2. Pharmacokinetic Statistical Inference

Pharmacokinetic parameter estimates will be evaluated to delineate effects of formulation. Log-transformed DN- $AUC(0-\infty)$ , DN- $AUC(0-t_{last})$ , and DN- $C_{max}$  will be evaluated in a linear fixed-effects model with a fixed effect for formulation. For the primary endpoint, a model comparing the differences between the [REDACTED] LY3074828 solution formulation and the [REDACTED] LY3074828 lyophilized formulation will be used. For the secondary endpoints, a model comparing the differences between the [REDACTED] LY3074828 solution formulation and the [REDACTED] LY3074828 lyophilized formulation, and between the [REDACTED] and [REDACTED] LY3074828 solution formulations will be used. Differences will be back-transformed to present the ratios of geometric least squares means and the corresponding 90% CI. If leakage occurs frequently, whether injection-site leakage occurred (yes/no) may also be included as a covariate in the model. Furthermore, if leakage is found to be significant, the amount of leakage will also be added to the model.

The  $t_{max}$  will be analyzed using a Wilcoxon rank sum test. Estimates of the median difference, 90% CIs, and p-values from the Wilcoxon rank sum test will be calculated.

Additional PK analyses may be conducted if deemed appropriate.

### **10.3.3. Pharmacodynamic Analyses**

This section is not applicable for this study.

### **10.3.4. Pharmacokinetic/Pharmacodynamic Analyses**

This section is not applicable for this study.

### **10.3.5. Evaluation of Immunogenicity**

The frequency of formation of antibodies to LY3074828 will be determined.

Treatment-emergent ADAs are those that are induced or boosted by exposure to study drug, with a 4-fold increase in titer compared to baseline if ADAs were detected at baseline, or a titer 2-fold greater than the minimum required dilution (1:10) if no ADAs were detected at baseline.

If a neutralization assay is performed, the frequency of neutralizing antibodies will be determined. The relationship between the presence (or absence) of antibodies and clinical parameters (AEs) will be assessed. Likewise, the relationship between the presence of antibodies and the PK parameters to LY3074828 will be assessed.

### **10.3.6. Exploratory Analysis**

Incidence of erythema, induration, categorical pain, pruritus and edema will be listed and summarized by treatment.

The 0 hour (post-injection) pain score will be evaluated in a linear fixed-effects model with a fixed effect for treatment. The distribution of the data will be explored prior to analysis to determine whether data transformation is required. The differences between the 1.5 mL and 1.0 mL injections for the lyophilized formulation will be back-transformed (if applicable) to present the ratios of geometric least squares means and the corresponding 90% CI. It is possible that the pain scores will be 0 so if the distribution of the data implies that a log-transformation is required then the score may be updated to  $\log(VAS+1)$  to allow for the inclusion of the 0 values in the analysis.

Leakage data will be summarized by treatment using descriptive statistics and may be used as a covariate in the PK analyses.

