Injection-site pain based on VAS (hour)		0, 0.5, 1, 3, 6	24												Performed for both injections of lyophilized formulation into the lower quadrants (ie, first 2 injections), and for the first injection of solution formulation (administered to a lower quadrant). 0 hour assessments to be performed within 1 minute following injection. Time allowance for 0.5 and 1 hour will be $\pm 5$ minutes and all other time allowances will be $\pm 15$ minutes.
Injection-site leakage and bleeding assessment (hour)		0													Performed for both injections of lyophilized formulation into the lower quadrants (ie, first 2 injections), and for the first injection of solution formulation (administered to a lower quadrant). 0 hour assessments to be performed within 1 minute following injection.
LY3074828 pharmacokinetic sampling (hour)		0, 2, 6	24	72	168	240	336	504	672	1008	1344	1680	2016		Times with respect to start of dosing. 0 hour collection immediately (within 15 minutes) before dosing. Time allowance for 2, 6, and 24 hour timepoints: $\pm 15$ , $\pm 30$ , and $\pm 90$

Procedure	Screening	Days													Comments	
		$\leq 28$ days	-1	1	2	4 $\pm 1$ d	8 $\pm 1$ d	11 $\pm 1$ d	15 $\pm 2$ d	22 $\pm 2$ d	29 $\pm 2$ d	43 $\pm 2$ d	57 $\pm 3$ d	71 $\pm 3$ d	85/ED $\pm 3$ d	
Immunogenicity sample																minutes respectively.
Pharmacogenetics sample		X														LY3074828 antibody sample.

Abbreviations: AE = adverse event; BMI = body mass index; CRU = clinical research unit; d = day; ECG = electrocardiogram; ED = early discontinuation; FSH = follicle-stimulating hormone; ICF = informed consent form; TB = tuberculosis; VAS = visual analog scale.

Site should schedule activities as appropriate. In cases where several study procedures are scheduled at the same time, follow this order of priority for procedures: pharmacokinetic samples, ECG, vital signs, clinical laboratory tests, VAS, injection-site leakage assessment, injection-site assessment, immunogenicity sample, stored sample, such that PK sample collection occurs as close to the nominal collection time as possible. Procedures specified as predose may be performed within 2 hours from planned dosing.

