**Table AMAE.1. Objectives and Endpoints**

Objectives	Endpoints
Primary To evaluate the relative bioavailability of LY3074828 solution formulation in PFSs and lyophilized formulation.	The ratio of geometric least square means between the CCI LY3074828 solution formulation supplied in the PFSs and the CCI LY3074828 lyophilized formulation for area under the concentration-time curve from time 0 extrapolated to infinity (AUC[0- $\infty$ ]), and area under the concentration-time curve from time 0 to the time of last measurable concentration (AUC[0-t last ]).
Secondary To evaluate the relative bioavailability of CCI and CCI LY3074828 solution formulations, and CCI LY3074828 solution formulation in PFSs and CCI LY3074828 lyophilized formulation.  To assess the tolerability of LY3074828 in healthy subjects.	The ratio of geometric least square means between the CCI and CCI LY3074828 solution formulations supplied in PFSs, and between the CCI LY3074828 solutions formulation supplied in PFSs and the CCI LY3074828 lyophilized formulation, for AUC(0- $\infty$ ) and AUC(0-t last ).  Incidence of treatment-emergent adverse events (TEAEs). Incidence of treatment-emergent anti-drug antibodies (TE-ADAs).
Exploratory To assess local tolerability and leakage of a LY3074828 lyophilized formulation and solution formulations supplied in PFSs at injection-sites.	Assessments of pain (using a visual analog scale). Incidence of erythema, induration, categorical pain, pruritus, edema, and leakage at injection-sites.

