**Table AMAE.2. Treatments Administered**

Treatment arm	Lyophilized formulation CCI [REDACTED]	Pre-filled syringes CCI [REDACTED]	Pre-filled syringes CCI [REDACTED]
Reference/test	Reference	Test 1	Test 2
Product	LY3074828	LY3074828	LY3074828
Dose	CCI [REDACTED] a	CCI [REDACTED]	CCI [REDACTED]
Concentration	CCI [REDACTED]	CCI [REDACTED]	CCI [REDACTED]
Injection volumes	CCI [REDACTED] CCI [REDACTED] CCI [REDACTED]	CCI [REDACTED] CCI [REDACTED]	CCI [REDACTED] CCI [REDACTED]
Number of injections	3	2	4
Formulation and presentation	Lyophilized powder for reconstitution	Solution in a PFS	Solution in a PFS

Abbreviations: PFS = pre-filled syringe.

a Theoretical total dose = 252 mg

Injection-sites selected for SC administration should be in the abdominal region approximately 5 cm from the umbilicus, and treatment should be administered with the needle applied at approximately 45 degrees with pinching the skin. Subcutaneous administration of LY3074828 should be given by a limited number of individuals for consistency. The same type of syringe and needle (27-gauge, half-inch needle) should be used for all subjects to ensure all injections are delivered to a consistent depth target into the SC space. Subsequent injection(s) should be given immediately following the previous injection.

For the lyophilized formulation (Reference), the [CC1] injection and the first of the [CC1] injections will be given into lower quadrants of the abdomen. The remaining [CC1] injection will be administered into an upper quadrant. The order and location of the first 2 injections will be randomized (see Section 7.2).

For administration of the [CC1] solution formulation in PFSs (Test 1), injections will be given into separate lower quadrants of the abdomen. For administration of the [CC1] solution formulation in PFSs (Test 2), the first 2 injections will be given into separate lower quadrants of the abdomen, and the final 2 injections will be given into separate upper quadrants of the abdomen.

Further information around SC administration will be in pharmacy handling instructions.

Investigational products will be prepared at the site by pharmacists or other trained personnel. Investigational products will only be administered to subjects on-site by nurses or other appropriately trained personnel.

The investigator or designee is responsible for:

- explaining the correct use of the investigational products to the site personnel
- verifying that instructions are followed properly

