#### **9.4.6. *Injection-Site Assessments***

Injection-site reactions will be evaluated through the collection and review of TEAEs and through the use of an Injection-Site Reaction Follow-up Form completed by the investigator. Local tolerability at the injection-sites will be examined by evaluation of erythema, induration, categorical pain, pruritus, and edema as indicated in Section 2. For each event, the severity, duration, and timing of the event in relation to the administration of study drug will be recorded. If one or more symptom(s) of an injection-site reaction is reported during the assessment, a single AE for injection-site reaction will be recorded on the AE page of the eCRF.

Pain assessments will help to determine if injection volume (1.0 mL versus 1.5 mL) is a contributing factor. For the lyophilized formulation, injection-site assessments of pain and leakage will be performed for the 2 injections in the lower quadrants of the abdomen (1.0 mL and 1.5 mL injections). For both dose levels of solution formulation in PFSs, injection-site assessments of pain and leakage will be performed for the first injection, which will be administered into a lower quadrant of the abdomen.

Pain measurements will be quantified using a 100-mm validated visual analog scale (VAS). The VAS is a well-validated tool (Williamson and Hoggart 2005) for the assessment of injection-site pain, and is presented as a 10-cm (100-mm) line, anchored by verbal descriptors, usually “no pain” and “worst imaginable pain.” The subject will be asked to rate any pain on a scale of 0 to 100 mm on the line immediately (within 1 minute) following the start of the injection and at time points according to the Schedule of Activities (Section 2).

Injection-site leakage will be assessed using pre-weighed filter paper, blotting the injection-site immediately after the injection to absorb any post-injection leakage and placing the filter paper back on the tared analytical balance in a similar manner as previously described (Ignaut and Fu 2012). The amount of leakage will be calculated by subtracting the pre-weighed filter paper measurement from the post-injection-site blot filter paper measurement. Any bleeding from the injection-site will also be documented.

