3. INTRODUCTION

This SAP has been developed after review of the Clinical Study Protocol (final version dated 05 April 2017).

This SAP describes the planned analysis of the safety, tolerability and pharmacokinetic (PK) data from this study. A detailed description of the planned TFLs to be presented in the clinical study report (CSR) is provided in the accompanying TFL shell document.

The intent of this document is to provide guidance for the statistical and PK analyses of data. In general, the analyses are based on information from the protocol, unless they have been modified by agreement between Eli Lilly and Company and Covance Early Clinical (EC) Biometrics. A limited amount of information concerning this study (e.g., objectives, study design) is given to help the reader's interpretation. This SAP must be signed off prior to first subject administration for this study. When the SAP and TFL shells are agreed upon and finalized, they will serve as the template for this study's CSR.

This SAP supersedes the statistical considerations identified in the protocol; where considerations are substantially different, they will be so identified. If additional analyses are required to supplement the planned analyses described in this SAP, they may be performed and will be identified in the CSR. Any substantial deviations from this SAP will be agreed upon between Eli Lilly and Company and Covance EC Biometrics and identified in the CSR. Any minor deviations from the TFLs may not be documented in the CSR.

This SAP is written with consideration of the recommendations outlined in the International Conference on Harmonisation (ICH) E9 Guideline entitled Guidance for Industry: Statistical Principles for Clinical Trials¹ and the ICH E3 Guideline entitled Guidance for Industry: Structure and Content of Clinical Study Reports².

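### The protocol's pain model names no subject term for the within-subject 1.5 mL versus 1.0 mL contrast, so its 90% CI is too wide if the paired scores correlate positively; SAP 9.4.12 also conflicts with that contrast

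*Protocol*

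**What the plan says.** Protocol 9.4.6 gives the purpose: "Pain assessments will help to determine if injection volume (1.0 mL versus 1.5 mL) is a contributing factor". For the lyophilized (Reference) arm, the Schedule of Activities says of the VAS assessment: "Performed for both injections of lyophilized formulation into the lower quadrants (ie, first 2 injections"). One of these injections is 1.0 mL and the other 1.5 mL. Protocol 7.1 adds: "The order and location of the first 2 injections will be randomized", and 7.2 sets out four sequences for doing so. The pre-filled syringe arms differ: "For both dose levels of solution formulation in PFSs, injection-site assessments of pain and leakage will be performed for the first injection". A Reference subject therefore gives two 0-hour scores and a syringe subject gives one.

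Protocol 10.3.6 states the analysis: "The 0 hour (post-injection) pain score will be evaluated in a linear fixed-effects model with a fixed effect for treatment". It continues: "The differences between the 1.5 mL and 1.0 mL injections for the lyophilized formulation will be back-transformed (if applicable") and reported with a 90% CI. A log(VAS+1) transformation is allowed for. The Synopsis gives the same model. Protocol Section 4 lists pain as an exploratory endpoint.

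SAP Section 3 says: "This SAP supersedes the statistical considerations identified in the protocol; where considerations are substantially different, they will be so identified". The body of SAP 9.4.7 (Injection Site Pain Assessment) is redacted. SAP 9.4.12, the statistical methodology clause for safety and tolerability, says that no inferential analysis is planned. SAP Section 11 declares no change from the protocol's analyses.

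**The concern.** The design puts both volumes in the same subject, with order and side randomized. The stated model does not use that. A fixed-effects model whose only named term is treatment treats all scores as independent, including the two from one person. The same form of model suits the PK parameters, where each subject contributes one value per parameter, but not this contrast.

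If the two scores correlate positively, as one would usually expect of two ratings by one person, the interval is wider than the data warrant and the benefit of pairing is lost. If they correlate negatively, it is too narrow. Either way the CI misstates how well the trial answers its own question about injection volume.

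The second matter is consistency. A modelled difference with a CI is inferential. The protocol plans one, SAP 9.4.12 excludes it, and SAP Section 11 says that nothing changed.

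**Working it through.** **Figures in the documents.** None is given for the pain contrast. The only stated precision figure is for PK (Protocol 10.1): a 90% CI half-length of about 0.32 on the log scale, with 90% probability, 16 per arm and CV 49%. It reproduces. σ = √ln(1 + 0.49²) = 0.4639, and with 30 df the half-length is t(0.95) × σ × √(2/16) × √(χ²(0.90)/30) = 0.3225. It says nothing about pain.

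**Inputs.** 18 Reference subjects randomized (Protocol 5.1), 16 expected to be evaluable (10.1), two scores per Reference subject (9.4.6), 90% CI (10.3.6). The within-subject correlation ρ and the VAS standard deviation are not given. ρ is varied and widths are in SD units.

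**Formulas, n pairs, equal variances.**
- No subject term, Reference scores only: half-width = t(0.95, 2n−2) × √(2/n). For n = 18: 1.6909 × 0.3333 = 0.564 SD, whatever ρ is.
- Paired: half-width = t(0.95, n−1) × √(2(1−ρ)/n). For n = 18 and ρ = 0.5: 1.7396 × √(1/18) = 0.410 SD.
- The standard error without the subject term is 1/√(1−ρ) times the correct one: 1.41 at ρ = 0.5.

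**Simulation.** 60,000 trials per setting, bivariate normal scores, n = 18. Mean half-widths are slightly below the formula values because they use estimated SDs. The mean half-width without a subject term is 0.56 SD throughout.

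| ρ (assumed) | Paired mean half-width (SD) | Width without subject term ÷ paired | Coverage without subject term |
|---|---|---|---|
| −0.3 | 0.65 | 0.86 | 85.2% |
| 0 | 0.57 | 0.98 | 89.9% |
| 0.3 | 0.48 | 1.17 | 94.7% |
| 0.5 | 0.40 | 1.38 | 97.5% |
| 0.8 | 0.26 | 2.18 | 99.9% |

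The paired interval covers 89.8% to 90.1% at every ρ tried.

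**Sensitivity.**
- n = 16: coverage 85.2%, 90.0%, 94.9% and 97.6%, with ratios 0.86, 0.98, 1.17 and 1.38, at ρ = −0.3, 0, 0.3 and 0.5.
- log(VAS+1), n = 18, with VAS = round(exp(2.2 + 1.2z) − 4) limited to 0–100 mm (28% zeros), ρ being the correlation of z: coverage 85.7%, 89.9%, 94.5% and 97.2%, with ratios 0.87, 0.98, 1.15 and 1.35.
- All arms in one four-level model (68 df, n = 18): mean half-width 0.554 SD, with ratios 1.16 and 1.37 at ρ = 0.3 and 0.5.
- The paired interval has fewer degrees of freedom, so it is the shorter one on average only once ρ exceeds about 0.04 (two-level model) or 0.06 (four-level model) at n = 18. Below that the widths are nearly equal.
- A random subject intercept with its variance bounded at zero covers 86.1%, 88.7%, 89.7% and 89.9% at ρ = −0.3, 0, 0.3 and 0.5. It deals with positive correlation but not negative.

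**SAP consistency.** There are two cases. If 9.4.7 keeps the protocol's contrast and CI, then 9.4.12 is wrong as written. If 9.4.7 drops them, then Section 11 is incomplete, because Section 3 says that substantial differences will be identified.

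**The case against.** The strongest reply is that the SAP governs and its pain section is redacted. SAP 9.4.7 may already contain a subject term, so the visible text cannot show that the analysis finally planned ignores the pairing. That stands, and the point is confined to the model as the protocol words it.

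The protocol sentence can also be called shorthand: a treatment factor with three arms cannot produce a volume contrast within one arm, so some recoding must be intended. That is fair. But recoding treatment into four levels still leaves no subject term, and calling the model fixed-effects points away from a random one.

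On the SAP conflict, 9.4.11 bars statistical analysis only of assessments that the section does not detail, which suggests that detailed ones may be analysed. 9.4.12 could then mean no inference beyond the preceding subsections. The reading is possible, but 9.4.12 is the methodology clause for the whole of 9.4, as 9.3.2 is for PK, and it makes no exception.

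Finally, the consequence is slight. With positive correlation the interval is conservative, no decision rule depends on it, and the sizes rest on assumed correlations. All of this is true and is why the grade is minor.

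**Conclusion.** The concern holds, as a minor point. As the protocol is worded, the 90% CI for the 1.5 versus 1.0 mL pain difference ignores the pairing. At assumed correlations of 0.3 to 0.5 with 18 pairs it is 1.17 to 1.38 times as wide as it should be and covers 94.7% to 97.5%. At −0.3 it under-covers, at 85.2%. These sizes assume equal variances. The estimate is unbiased with complete pairs, and the primary PK comparison and the sample size are untouched. What SAP 9.4.7 finally specifies cannot be seen; if it handles the pairing, only the protocol wording is incomplete. The mismatch between SAP 9.4.12, SAP Section 11 and the protocol needs a correction in either case.

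**What to change.** - **Protocol 10.3.6, the Synopsis and SAP 9.4.7:** state that, in Reference subjects, the 1.5 mL minus 1.0 mL difference in 0-hour VAS score (or log(VAS+1)) is estimated from within-subject paired differences and reported with its 90% CI. A mixed model with injection volume and an unstructured within-subject covariance is an acceptable equivalent. A term for injection order is optional.
- **Syringe arms:** keep any comparison with them in a separate treatment model, or include the subject term if all scores go into one model.
- **If SAP 9.4.7 already does this:** bring the protocol wording into line with it.
- **SAP 9.4.12 or Section 11:** add an exception to 9.4.12 for the 0-hour pain contrast in 9.4.7. If the contrast was dropped, record that in Section 11.

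The cost is wording and a few lines of code, with no new data. If the true correlation is zero, the paired interval at n = 18 is about 2% wider than the two-level one (0.572 against 0.560 SD) and about 3% wider than the four-level one (0.572 against 0.554 SD).

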## 7.2. Method of Treatment Assignment

Subjects will be randomized to 1 of 3 treatment arms (CC1 LY3074828 lyophilized formulation [Reference], CC1 LY3074828 solution formulation [Test 1], or 500 mg LY3074828 solution formulation [Test 2]). Those that are randomized to receive the lyophilized formulation will be further randomized to 1 of 4 treatment sequences:

Sequence	First Injection	Second Injection
1	CC1 administered into left lower quadrant	CC1 administered into right lower quadrant
2	CC1 administered into right lower quadrant	CC1 administered into left lower quadrant
3	CC1 administered into left lower quadrant	CC1 administered into right lower quadrant
4	CC1 administered into right lower quadrant	CC1 administered into left lower quadrant

For all sequences, the third injection will comprise a 1.0 mL injection administered into an upper quadrant.

Randomization will be performed using a computer-generated randomization schedule.

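### The 0-hour pain model leaves out injection order, side and subject: the volume contrast loses precision, and any lyophilized-versus-solution pain comparison carries a position shift

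*Protocol*

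**What the plan says.** Protocol 10.3.6 (repeated in the synopsis) gives the model for the VAS score taken just after injection: "The 0 hour (post-injection) pain score will be evaluated in a linear fixed-effects model with a fixed effect for treatment". The one contrast it undertakes to report, with a 90% CI, is 1.5 mL against 1.0 mL within the lyophilized arm. Protocol 9.4.6 gives the reason: "Pain assessments will help to determine if injection volume (1.0 mL versus 1.5 mL) is a contributing factor".

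The design around that model is richer:

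- Protocol 7.2: "Those that are randomized to receive the lyophilized formulation will be further randomized to 1 of 4 treatment sequences". Protocol 7.1 explains that these vary the order and location of the first two injections. The volumes in the sequence table are blacked out.
- Protocol 9.4.6, Reference: "For the lyophilized formulation, injection-site assessments of pain and leakage will be performed for the 2 injections in the lower quadrants of the abdomen".
- Protocol 9.4.6, both solution arms: "injection-site assessments of pain and leakage will be performed for the first injection, which will be administered into a lower quadrant".
- Protocol 7.1 has each further injection follow the previous one at once. It describes no randomisation of side in the Test arms.

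The exploratory objective (Protocol Table AMAE.1) covers local tolerability of both formulations, with VAS pain as an endpoint. SAP 9.4.7 is the pain section, but its text is blacked out. SAP 9.4.12 plans no inferential analysis of safety and tolerability, and SAP section 11 declares no departure from the protocol's analyses.

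**The concern.** The trial randomises order and side for the Reference injections and then names neither in the model. It also collects two ratings per Reference subject and names no subject term, so paired scores would be analysed as if they were independent.

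A second abdominal injection given straight after the first may be scored differently, through sensitisation, anticipation or anchoring on the first score. Two consequences follow if it is. In the volume contrast, the shift goes into residual error. In any comparison of lyophilized with solution, the Reference mean averages first and second positions while a Test mean contains first positions only. Randomising order within Reference cannot repair that, because the Test arms have no second-position ratings.

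At stake are the precision of the question that the pain scores were collected to answer, and the reading of pain by formulation.

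**Working it through.** **Plan's own figure.** The documents give no sample size or precision for pain. The 0.32 in Protocol 10.1 concerns AUC and Cmax. It reproduces: log-scale SD = sqrt(ln(1 + 0.49²)) = 0.4639, and with 16 per arm and 30 df the 90% CI half-length at 90% assurance is 0.3225. It says nothing about VAS.

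**Inputs.** From the documents: 18 subjects per arm (Protocol 5.1), four sequences in Reference (7.2), two rated injections per Reference subject and one per Test subject (9.4.6). Assumed, because no document gives them: an additive second-minus-first shift d of 0 to 20 mm; VAS SD of 15 mm between and 12 mm within subjects. Treatment is read as having separate levels for the two lyophilized volumes, since otherwise the named contrast could not be estimated.

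**1. Volume contrast, bias.** If k of n Reference subjects receive 1.5 mL first, the bias is d(n − 2k)/n.

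- Expected value under randomised order: 0.
- Split of 5/5/4/4 over the sequences: k is 8, 9 or 10, so the bias is at most 2d/18 = 0.11d, or 1.1 mm at d = 10 mm.
- Sixteen subjects at 4 per sequence: exactly 0.
- The protocol does not state how evenly sequences are allocated. With unrestricted allocation, the chance imbalance would have SD d/sqrt(18) = 0.24d, still centred on 0.

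**2. Volume contrast, cost of omitting position.** Each Reference rating is second with probability one half, so position adds d²/4 to its variance. Take a difference SD of 20 mm with no between-subject variance, the case in which the cost is greatest. The variance per rating is then 400/2 = 200, and the CI widens by sqrt(1 + (d²/4)/200):

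- d = 5: sqrt(1.031) = 1.02
- d = 10: sqrt(1.125) = 1.06
- d = 15: sqrt(1.281) = 1.13

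Between-subject variance dilutes this.

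**3. Volume contrast, cost of omitting subject.** With SDs of 15 and 12 mm and d = 0:

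- Treatment-only: variance per rating 225 + 144 = 369; SE = sqrt(2 × 369/18) = 6.40 mm; half-width about 1.675 × 6.40 = 10.7 mm.
- Within subject: SE = sqrt(2 × 144/18) = 4.00 mm; half-width about 1.753 × 4.00 = 7.0 mm.

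A simulation (4,000 trials per setting, 18 per arm, one Test arm) agrees. The treatment-only half-width is 10.65 mm at d = 0 and 11.63 mm at d = 20, a rise of 11.63/10.65 = 1.09, with coverage about 99% for a nominal 90%. With order, side and subject included it is about 6.9 mm, with coverage about 90%. Simulated bias stayed within about 0.2 mm of 0. The missing subject term therefore costs more than the missing position term.

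**4. Reference versus Test.** The bias is d times the share of second injections in Reference. Pooled over both volumes that share is exactly one half; for 1.0 mL alone it is 8/18 to 10/18 under the 5/5/4/4 split. Coverage is for the 90% CI of Reference 1.0 mL against Test, from the same simulation:

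| d (mm) | Bias d/2 (mm) | Coverage |
|---|---|---|
| 5 | 2.5 | about 87% |
| 10 | 5 | about 81% |
| 20 | 10 | about 60% |

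**The case against.** The strongest reply is that the only contrast named in Protocol 10.3.6 lies wholly within Reference, where order and side are randomised. A reader might infer from the omitted terms that volume is confounded with injection position. The documents do not support that: each volume is as likely to come first as second, and step 1 shows zero expected bias. This part of the objection stands in full.

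Two further inferences also fail. Dropout does not unbalance the order, because the score is taken within a minute of injection on Day 1 and Protocol 10.3 keeps all dosed subjects in the safety analyses. CI widening of 3%, 12% and 25% for d = 5, 10 and 15 mm, from sqrt(1 + (d/20)²), belongs to a paired analysis without position. Under the treatment-only model the figures are those in step 2.

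It is also fair to say that no lyophilized-versus-solution pain contrast is specified. The d/2 shift therefore attaches to a comparison that the protocol does not name. What remains is that the exploratory objective covers both formulations and a treatment-level model yields their means side by side, so readers are likely to compare them.

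Lastly, SAP 9.4.7 cannot be read and may contain more terms. The SAP supersedes the protocol's statistics, but it undertakes to identify substantial differences and its section 11 reports none. The point therefore stands against the protocol text, and not as a finding about the hidden section.

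**Conclusion.** The point holds in a limited form. As written in the protocol, the pain model discards the pairing and the randomised order and side. The volume contrast remains unbiased in expectation, but its interval is too wide: about 10.7 to 11.6 mm where about 6.9 mm is attainable under the assumed SDs. Any formulation comparison of pain moves by about d/2.

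The sizes depend on d and the VAS SDs, which no document supplies; if d is zero, the formulation shift vanishes and only the loss from ignoring pairing remains. Reading the four sequences as order by side rests on Protocol 7.1, because the volumes in the 7.2 table are blacked out. The endpoint is exploratory and the primary PK comparison is untouched, so this is an inexpensive improvement and not a threat to the trial's main conclusion.

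**What to change.** In Protocol 10.3.6 and, if it does not already say so, SAP 9.4.7:

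1. For 1.5 versus 1.0 mL, fit the Reference ratings with volume, injection position (first/second), side (left/right) and a subject effect. Keep the side term to arms where side is recorded, since no side randomisation is described for the Test arms.
2. For any lyophilized-versus-solution pain comparison, use first injections only: the roughly 9 Reference subjects whose 1.0 mL injection came first, against the first injection in each Test arm. Alternatively, adjust for position and state that the shift is assumed additive.
3. Show the 0-hour VAS by volume and position.
4. Reconcile the model and 90% CI of Protocol 10.3.6 with SAP 9.4.12, which plans no inferential analysis, and with SAP section 11, which declares no change.

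The cost is some wording, one table and a few degrees of freedom. For Reference, both design factors are already in the randomisation schedule. The first-injection formulation comparison will be imprecise, with about 9 Reference subjects against 18 per Test arm, but it is free of the position shift.
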